8.3.2 Imupret® oral solution

The composition of the medicinal product is as follows:

Active substances: 100 g drops contain 29 g of an alcoholic aqueous extract (extracting agent: ethanol 59% (V/V) made from the following medicinal plants:

Marshmallow root (Radix Althaeae)	0,4 g;
Camomile flowers (Flores Chamomillae)	0,3 g;
Horstail herb (Herba Equiseti)	0,5 g;
Walnut leaves (Folia Jungladis)	0,4 g;
Yarrow herb (Herba Millefolii)	0,4 g;
Oak bark (Cortex Quercus)	0,2 g;
Dandelion herb (Herba Taraxaci)	0,4 g;

Excipients: Ethanol 19 % (V/V), purified water.

Pharmaceutical form: Oral drops.

Clear or slightly turbid yellow-brown fluid with characteristic taste and chamomile aroma. Turbidity or flocculation may occur during storage.

Name and address of the manufacturer.

Bionorica SE, [name].

Indications. Diseases of the upper respiratory passages (tonsillitis, pharyngitis, laryngitis). Prevention of complications and recurrences in patients with respiratory viral infections caused by the reduced resistance of the organism.

Age	Dosage for acute symptoms	Dosage after acute symptoms have subsided and for prophylactic treatment
Children of 1 year of age	5 drops 5 – 6 times daily	5 drops 3 times daily
Children from 2 to 5 years	10 drops 5 – 6 times daily	10 drops 3 times daily
Children from 6 to 11 years	15 drops 5 – 6 times daily	15 drops 3 times daily
Adults and adolescents from the age of 12 years	25 drops 5 – 6 times daily	25 drops 3 times daily

However, only patients from the age of 6 upwards will be included in the trial.

8.3.3 Reference treatment

All patients of the trial will undergo the reference treatment described below. However, only one of the two study groups (study group 1) will receive and add-on treatment with either Imupret® oral solution (see 0 and 8.3.2).

Reference treatment comprises instructions for patient's behavior as well as possible medical treatment when needed:

- Sparing diet with fractional feeding (5-6 times a day) in only small portions explicitly excluding coarse, spicy, or heavily digestible food
- At the discretion of the investigator, elimination of all factors irritating pharyngeal mucosa (e.g. thermal, chemical influence etc.)

At the discretion of the investigator, Paracetamol as single doses up to 500 mg – not more than 3-4 times daily

- At the discretion of the investigator, topical treatment like benzydamine, lidocaine (in case of severe sore throat)
- At the discretion of the investigator, antibiotic treatment in case it is indicated with e.g. amoxicillin clavulanate, cephalosporins (in case of prescription of antibiotics patients will be evaluated separately)

8.3.4 Concomitant medication not allowed

Patients need to be withdrawn from the study in case of the administration of the following medication groups:

- Inhaled and systemic corticosteroids
- Interferon preparations
- Antiviral drugs
- Immunomodulators
- Antihistamines

Patients may be withdrawn following the intake of any medication which, at the discretion of the investigator, might interfere with the objectives of the trial.

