
Sample size calculation
	
Justification of the number of subjects
 
This trial is parallel, two-group, with the same size groups.
 
The planned test power is 80% (the probability of making a second kind error is 0.2), the two-way probability of making a type 1 error is 0.05. The sample size was estimated by the main variable of the clinical trial.
 
Thus, this trial was a comparative for superior efficiency.
 
When proving superior therapeutic efficacy, the following statistical hypotheses are tested:
 
H0: e £ d versus On: e > d, where d is the limit of greater efficiency — the marginal value of clinically important differences, at which it can be considered that the tested drug exceeds its effectiveness by control (in this study it was taken equal to 15%); e - estimated (observed) differences between groups in therapeutic efficacy.
 
Given that the main variable is dichotomous, the size of each group can be estimated using the following expressions:
 
n control = k · n main
 $n_{main} = \frac{(z_{\alpha} + z_{\beta})^2}{(\varepsilon - \delta)^2} \cdot \left[\frac{p_{control} \cdot (1 - p_{control})}{k} + p_{main} \cdot (1 - p_{main}) \right]$ 
where: z_{α} and z_{β} —the corresponding percentage points of the standard normal distribution; d - the minimum acceptable value of clinically important differences; e - presumed (observable) differences between groups on therapeutic efficacy (the difference between the shares of positive results in groups); pcontrol and p main —shares of positive results in the

main and control groups, respectively; k - coefficient for unequal number of patients in groups (control is greater than the main); n_{main} и $n_{control}$ - the planned number of patients in the main and control groups, respectively; α is the boundary value of the error of the 1st kind (level of significance); β - is the boundary value of the error of the second kind.

In the planned study, it was assumed that the number of patients in the main and control groups was the same ($k = 1$), the significance level was $\alpha = 0.05$ (two-sided); the boundary value of the error of the second kind is $\beta = 0.2$ (which makes it possible to achieve a research power of 80%). Baseline data and the results of calculations using the above formula are given in Table. 1.

Table 1 - Baseline and Sample Size Estimation Results

Statistical indicator	Value of the indicator
Multiplicity factor k	1

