Boundary probability error of the first kind α	0,025
The probability of an error of the second kind β	0,2
The percentage point S.N.R. for α	1,96
The percentage point S.N.R. for β	0,84
The observed frequency of the positive effect for the control group $p_{control}$	0,75
Estimated value of the positive effect for the main group p_{main}	0,90
The value of the clinically important differences d	0,15
Estimated differences between groups e	0,0
The size of the main group n_{main}	97
The size of the control group $n_{control}$	97
Estimated share of departures	3
Adjusted main group size	100
Adjusted control group size	100

The final number of patients in each group was adjusted for their possible dropout. Thus, the final number of subjects in each group was 100 patients (200 patients in total).

Test treatment	
 - Treatment with Imupret® oral drops according to the respective Summary of Product characteristics (Imupret® coated tablets or oral drops during acute period for 5 days, afterwards switch to the subacute dosage regimen for further 28 days) - Sparing diet; fractional feeding (5-6 times a day) in small portions with the exception of coarse, spicy, heavily digestible foods - Elimination of factors irritating pharyngeal mucosa (thermal, chemical) 
 - As needed, Paracetamol (Acetaminifen) in a single dose of up to 400 mg not more than 3 times daily or paracetamol in a single dose of up to 500 mg 3-4 times daily (if necessary). - Topical agents such as Benzydamine, Lidocaine as needed (in case of severe sore throat). 	
Reference treatment	
 - Sparing diet; fractional feeding (5-6 times a day) in small portions with the exception of coarse, spicy, heavily digestible foods - Elimination of factors irritating pharyngeal mucosa (thermal, chemical) - As needed, Paracetamol (Acetaminifen) in a single dose of up to 400 mg not more than 3 times daily or paracetamol in a single dose of up to 500 mg 3-4 times daily (if necessary). - Topical agents such as Benzydamine, Lidocaine as needed (in case of severe sore throat). 	
Investigational Medicinal Product	Active (add on) treatment	Imupret® oral drops

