9.4 Premature discontinuation

9.4.1 Withdrawal criteria for included patients

Patients may prematurely discontinue their participation in the trial at any time, without giving reasons and without any disadvantageous consequences for their subsequent medical care.

Patients can be withdrawn from the trial by the investigator for the following reasons:

- Withdrawal of consent
- Serious Adverse Events (SAEs) at the Principal Investigator's discretion
- Appearance of non-tolerable AE(s)
- Appearance of an exclusion criterion, which concerns the safety of the patient in the opinion of the investigator
- non-adherence to the trial conditions or relevant deviations from procedures with regard to medical aspects at the Principal Investigator's discretion
- Diseases, AEs requiring treatment that occur after inclusion, which do not constitute SAEs but which, in the opinion of the Principal Investigator, would probably prevent achievement of the clinical trial objectives or which unacceptably endangered the safety of the subject
- Poor compliance of the patient
- Patient lost to follow-up
- Pregnancy (females of childbearing potential)
- Any situation judged by the investigator to be more harmful for the patient if he/she remains in the trial
- Other reasons which in the opinion of the investigator justify withdrawal of a patient (e.g. not meeting inclusion criteria during screening period)

In all cases, the reason for and date of withdrawal from the trial as well as the day and time of last intake of IMP must be recorded in the CRF and in the patient's medical records.

The investigator must make every effort to contact patients lost to follow-up. Attempts to contact such patients must be documented in the patient's records (e.g. times and dates of attempted telephone contact, documentation for sending a registered letter etc.).

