9.4.2 Replacements

Patients withdrawn from the trial after randomization, regardless of the reason for withdrawal, will not be replaced.

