12.2.1 Analysis sets

Full Analysis Set (FAS)

The FAS consists of all randomized patients with at least one documented application of IMP and with at least one observed post-baseline value.

Per Protocol Set (PPS)

The PPS consists of all patients of the FAS without major protocol deviations. The evaluation of protocol deviations and whether they lead to the exclusion of a patient from the PPS will be performed during data review of the study.

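### Withdrawal from the study after a listed medication or poor compliance discards later efficacy outcomes, and no rule says how the missing outcomes are handled

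*Protocol*

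**What the plan says.** Protocol section 8.3.4 lists inhaled and systemic corticosteroids, interferons, antivirals, immunomodulators and antihistamines, and says: "Patients need to be withdrawn from the study in case of the administration of the following medication groups". This is mandatory and the same in both arms. The section then lets the investigator withdraw a child after any other medication thought to interfere with the trial's objectives.

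Section 9.4.1 gives reasons for which a child can be withdrawn. They include "Poor compliance of the patient" and non-adherence to the trial conditions. These reasons are permissive and name neither a drug nor an arm. At withdrawal the investigator records the reason, the date and the last study drug intake; no efficacy assessment is asked for, then or later. Section 9.4.2 adds: "Patients withdrawn from the trial after randomization, regardless of the reason for withdrawal, will not be replaced".

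The full analysis set (Protocol 12.2.1, repeated in the SAP) requires a documented study drug application and keeps patients "with at least one observed post-baseline value". Neither document says how a missing outcome counts. Both leave the analysis specifications until after the database is closed. Section 8.4 confirms that there is no blinding.

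**The concern.** A child who leaves after visit 2 can remain in the full analysis set on visit 2 data, but has no local tonsillitis score at day 10 and, unless antibiotics were already prescribed, no settled responder status. If the reason for leaving is linked to poor progress, the children still observed at day 10 are a selected group.

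There are two plausible routes to such a link, both inferred. Some listed drugs may be given because a child is not improving. And discretionary withdrawals are decided with the arm known. In addition, non-compliance with Imupret itself can arise only in study group 1, although both arms have diet, avoidance of irritants and daily self-assessment forms to comply with.

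An as-observed comparison would then no longer be the randomised one, and no later analysis can recover outcomes that were never collected.

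**Working it through.** **Inputs from the documents.** Synopsis, sample size table: "The observed frequency of the positive effect for the control group" 0.75; "Estimated value of the positive effect for the main group" 0.90; critical values 1.96 and 0.84; 97 per group, raised to 100 for 3 departures. The synopsis text adds that "the two-way probability of making a type 1 error is 0.05".

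**The plan's own figure.** n = (1.96 + 0.84)² × [0.75×0.25 + 0.90×0.10] / 0.15² = 7.84 × 0.2775 / 0.0225 = 96.7, so 97; and 97 + 3 = 100. It reproduces.

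**Assumptions.** The documents give no withdrawal rate by arm or by outcome. The scenarios below are assumed: 100 randomised per arm, a responder comparison at day 10, and withdrawn children left out (as observed).

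**A. No true effect (75% in both arms), only Imupret failures lost.** With k failures lost, the observed Imupret rate is 75/(100 − k), against 75/100 in the reference arm. The false-finding chance is the exact binomial probability that an uncorrected chi-square test is significant in favour of Imupret at two-sided 0.05.

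| k lost | Imupret rate | Spurious difference | False finding for Imupret |
|---|---|---|---|
| 0 | 75.0% | 0 | 2.5% |
| 3 | 75/97 = 77.3% | +2.3 points | 5.7% |
| 5 | 75/95 = 78.9% | +3.9 points | 9.5% |
| 10 | 75/90 = 83.3% | +8.3 points | 29.4% |

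The row k = 3 equals the plan's own departure allowance per group. The rows k = 5 and 10 mean that 20% and 40% of the 25 Imupret failures leave and no reference failures do.

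**B. No true effect, 5 failures lost in each arm.** 75/95 against 75/95: difference 0, and the false-finding chance stays at 2.5%.

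**C. Planned effect, 20% of failures lost in both arms.** Imupret loses 2 of 10 (90/98 = 91.8%) and reference loses 5 of 25 (75/95 = 78.9%). The difference falls from 15 to 12.9 points. SE = √(0.918×0.082/98 + 0.789×0.211/95) = 0.0501; power = Φ(0.1289/0.0501 − 1.96), about 73%. With no losses the same formula at 100 per arm gives 81%.

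**D. Planned effect, 20% of reference failures lost only.** 90/100 against 75/95: 11.1 points. SE = 0.0515; power = Φ(0.1105/0.0515 − 1.96) = 57%, or 58% with the exact chi-square calculation.

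**E. Extreme bounds at the planned effect.** With w missing per arm and 90% and 75% success among those observed, the difference can lie anywhere in 0.15×(100 − w) ± w points: 11.6 to 17.6 for w = 3, 9.3 to 19.3 for w = 5, and 3.5 to 23.5 for w = 10.

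**F. Counting every missing outcome as failure.** With no true effect, if 5 or 10 reference children drop out for reasons unrelated to outcome, the reference rate becomes 0.75×95/100 = 71.3% or 0.75×90/100 = 67.5%. That is a spurious +3.8 or +7.5 points for Imupret, with a false-finding chance of 8.6% or 21.6%.

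**The case against.** The strongest reply is that the main route of treatment failure does not lead out of the study. Under delayed prescribing, failure means an antibiotic. Antibiotics are not on the section 8.3.4 list, their use is recorded, and the need for them is part of the main criterion. Those children are to be evaluated separately, which is a different question. This stands: it limits how many failures the withdrawal rules can remove.

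Other parts also stand. The medication rule is identical in both arms. Antihistamines or inhaled corticosteroids may be taken for unrelated conditions. Scores are to be evaluated per visit, so day 10 is not named as the only primary time point. The documents do not forbid assessment after withdrawal; they simply do not require it.

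A reader might infer that poor compliance is a withdrawal reason for the Imupret arm only, or that outcomes will certainly be lost selectively in Imupret's favour. The documents support neither. The compliance criterion is general and permissive; only non-compliance with Imupret itself is confined to group 1. Selective loss is a risk without stated rates, and scenarios B to D show that it can cancel or work against Imupret.

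What the reply does not remove is the gap itself. The duties to contact patients lost to follow-up (section 9.4.1) and to follow adverse events (section 11.2) do not restore efficacy outcomes.

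**Conclusion.** The concern holds as a risk that the plan creates and could cheaply avoid. A mandatory rule takes children out of the study after a listed medication, further withdrawals are discretionary in an unblinded trial, no efficacy outcome is required afterwards, and there is no missing-outcome rule.

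Neither size nor direction can be fixed from the documents. In the assumed scenarios the effect runs from no bias under balanced loss, through +2.3 points at the plan's own allowance of 3 if all were Imupret failures, to +8.3 points if 10 were. At the planned effect it shrinks the difference to between 12.9 and 11.1 points. All of this rests on an as-observed responder analysis at day 10, which the documents neither specify nor exclude.

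**What to change.** In sections 8.3.4 and 9.4.1, separate stopping treatment from leaving the study. Unless consent is withdrawn, children who use a listed medication or comply poorly should stay in the scheduled visit 2 to 5 assessments and be analysed in the arm to which they were randomised. Whether treatment is stopped remains a clinical decision.

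In the SAP, before database closure:

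- state how use of a listed medication for tonsillitis counts in the responder endpoint;
- for outcomes still missing, report the comparison as observed, with missing counted as failure in both arms, and under best-case and worst-case bounds.

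Missing-as-failure should not stand alone, because it biases the comparison when dropout differs by arm (scenario F).

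The cost is wording in two protocol sections, a short SAP addition, some extra follow-up effort and analysis, and possibly a slightly lower reported success rate. The visits are already scheduled.

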8.4 Randomization

The clinical part of the trial will be open and randomized with no blinding procedure. Subjects will be randomly assigned to one of the two possible treatments with according to the underlying randomization list. Randomization will be performed using [StatSoft – generator of random figures] software.

The appropriate number of the randomisation schedule and associated treatment will be allocated for each subject whose entry in the randomised part of the clinical trial is confirmed. The randomisation list will be part of the trial documentation.

8.5 Time schedule and visits

Four scheduled visits will be performed during the first phase of the study:

First study phase

- 1 visit (1st day): screening, randomization and treatment; evaluation by Mc Isaac Score scale; LTM Scale (Local Tonsillitis Manifestation Scale): (5 symptoms: Sore throat at swallowing (0 – absent, 1 – mild, 2 – moderate, 3 – severe / pronounced); Sore throat at rest; Throat irritation at rest; Palatine tonsils hyperemia; Palatine tonsils edema); Patients self-assessment (VAS; 0-10)

- 2 visit (3rd±1 day): intermediate evaluation of the effectiveness of treatment - clarification of the patient's condition, the need to prescribe an antibiotic; evaluation by LTM Scale, patients self-assessment (VAS; 0-10)
- 3 visit: intermediate evaluation of the effectiveness of treatment (day 5-day ±1) via telephone (or visit if necessary); patients self-assessment (VAS; 0-10)
- 4 visit: final (10th day ±1 day). Evaluation by LTM Scale (0-15), patients self-assessment (VAS; 0-10)
- 5 Follow up; day 28: evaluation of the long-term effects of treatment
- - An unscheduled visit can be made if the patient's condition worsens (according to the patient and / or the researcher, including if the symptoms of the disease persist or worsen, including but not limited to an increase in the temperature in the armpit above 38.0 ° C at the 3rd and / or subsequent days of treatment).
- The total duration of the treatment: 10 days
- The total duration of the study for one patient is not longer than 38 days.

Any unscheduled visit may be carried out in case of worsening of the patient's condition (at patient's and/or investigator's opinion), including persistence or aggravation of the disease symptoms.

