	Mode of administration and dosage regimen	
Imupret® oral drops
 
Dosage for acute symptoms:
 
Children from 6 to 12 years: 15 drops 5-6 times daily
 
Adults and adolescents from the age of 12 years: 25 drops 5-6 times daily
 
Dosage after acute symptoms have subsided:
 
Children from 6 to 12 years: 15 drops 3 times daily
 
Adults and adolescents from the age of 12 years: 25 drops 3 times daily

Duration of treatment	
Disease will be evaluated 36-48 hours prior to active treatment.
 
Active Imupret® treatment group: 10 treatment days
 
Reference treatment group: 10 days
 
Afterwards, there will be a follow up observation phase of 1 months
	

SCHEDULE OF ASSESSMENTS

V1		V2		V3 (Telephone call)					V4	V5
day 1	day 2	day 3	day 4	day 5	day 6	day 7	day 8	day 9	day 10	day 28

Study group 1

Imupret (dosage acute phase)
Reference treatment

Study group 2

Reference treatment

V1	day 1	Screening, randomization, prescription of treatment
V2	day 3	Status evaluation, possible prescription of antibiotics
V3	day 5 ±1	Evaluation of treatment efficacy, telephone call
V4	day 10 ±1	Evaluation of treatment efficacy, end of reference treatment
V5	day 28	Telephone call

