It should be noted that unjustified antibiotic therapy of acute tonsillitis is only based on the symptom "sore throat" or "exudate (plaque) tonsils" and plays a significant role in the formation of antibiotic resistance. Antibiotic therapy does not affect pain. In order to avoid the

irrational use of antibiotics, one should distinguish the desire of the patient or his parents to get rid of the pain, from the rational assessment of the doctor for all pros and cons about an antibacterial therapy.

To prevent unjustified prescription of antibiotics, a therapeutic concept of delayed administration is proposed. A patient with acute tonsillitis is prescribed treatment with antibacterial agents in a delayed manner (a prescription is written out, the dose and the frequency of administration is calculated). In the absence of positive effect within 36-48 hours from the beginning of treatment with Imupret the antibacterial therapy with antibiotics is started. The advantage of deferred antibiotic prescription is, that a higher number of patients and doctors, awaiting antibiotic therapy, may be more agreeable with this way of treatment than with a complete rejection of the antibiotics prescription. This is why delayed use of antibiotics is an important treatment strategy to reduce the number of unreasonable prescription of antibacterial agents.

Considering this fact, it becomes necessary to use drugs with a complex effect on the main processes of pathogenesis and have an evidence-based efficacy base for acute tonsillitis. At the present moment, there is an insignificant evidence base for the application of the phytonoering drug Imupret in acute tonsillitis. The spectrum of its pharmacological properties includes antiviral, antibacterial, antiinflammatory and immunomodulating effects. The combination of these properties makes it possible to influence practically all parts of acute tonsillitis. Additionally a good safety profile allows to consider Imupret as an adequate basic therapy for the treatment of acute tonsillitis, especially in the therapeutic concept of of delayed prescription of antibiotics. The already existing studies were not conducted under GCP conditions. Confirmation of the high effectiveness of Imupret in the treatment of acute tonsillitis would serve as a rationale for optimizing the treatment regimen of this nosology and recommendations for the inclusion of the drug in national guidelines.

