9.2 Inclusion criteria

- Children (males/females), 6 - 12 years old, with severe acute tonsillitis.
- Possibility to initiate therapy within 72 hours since the onset of the disease symptoms.
- Score 4-5 according to Mclsaac Scale.
- Patient's and (or) one of his/her parents' willingness and ability to fulfil the requirements of the Study Protocol.
- Signed informed consent of the patient and (or) his/her parents for participation in the study.

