10 METHODOLOGY

10.1 Screening examination - Visit 1

Screening examination will be performed prior to inclusion and prior to the first intended administration of the IMP to ensure that patients are eligible for the clinical trial.

The following assessments will be performed on Visit 1 (V1):

- demographic (age, sex, ethnic origin) and anthropometric data (body weight, height, BMI)
- medical history (including prior and concomitant medication)
- physical examination vital signs (blood pressure, pulse rate, body temperature (axillar))

Objective examination: skin and visible mucosa, palpation of abdomen and lymph nodes (submandibular, anterior and posterior cervical ones), oropharyngoscopy will be performed to assess the status of the tonsillitis.

Hence, objective symptoms included in the “Local Tonsillitis Manifestation Scale” are assessed using a 4-point rating scale using score “0” absent, “1” mild, “2” moderate, and “3” severe/pronounced. Diagnoses will be refined by using the Mclsaac Scale (see 0)

- clinical laboratory investigation: blood analysis including haematology, haemostatic system, serum chemistry, serology, urinalysis or other laboratory investigations are performed at the discretion of the investigator
- female status (in females with childbearing potential pregnancy test)

Finally, a self-assessment of the patient’s throat pain by him/herself and (or) his/her parent(s) using a visual analogue scale (VAS) is performed.

All data has to be documented by the investigator in the patient’s medical file and recorded in the CRF. Afterwards, inclusion and exclusion criteria are checked by the investigator, documented in the patient’s medical file, and recorded in the CRF.

At the end of Visit 1 the patient will be randomized, sorted to one of the two study groups and IMP will be handed over.

10.2 Status evaluation - Visit 2

The next status evaluation of the disease will be performed on day 3, i.e. ± 1 day after Visit 1 (V1).

A physical examination of vital signs (blood pressure, pulse rate, body temperature (axillar)) will be performed. All physical examinations done at V1 including skin and visible mucosa, palpation of abdomen and lymph nodes, oropharyngoscopy will be repeated to assess the status of the tonsillitis.

Again, objective symptoms included in the “Local Tonsillitis Manifestation Scale” are assessed and diagnoses will be refined by using the Mclsaac Scale (see 0).

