12.2.2 Primary endpoint

Main criterion for evaluation in the trial will be:

- Scores determined by the Local Tonsillitis Manifestations Scale refined by McIsaac's scale. Scores will be dichotomized to decide for two categories (therapy effective/therapy ineffective).
Scores will be evaluated by treatment and time point, i.e. per visit
- Need for an antibacterial therapy, i.e. number of patients per treatment.

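### The Visit 2 date can be settled anywhere from day 2 to day 4 after the arm is known, and nothing fixes it beforehand or reports actual visit day by arm

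*Protocol*

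**What the plan says.** Protocol section 8.5 gives the timing as "2 visit (3rd±1 day): intermediate evaluation of the effectiveness of treatment", and section 10.2 repeats day 3 with a one-day tolerance. Visit 4 is day 10, also ±1.

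On allocation, section 8.4 states "The clinical part of the trial will be open and randomized with no blinding procedure", and section 10.1 adds "At the end of Visit 1 the patient will be randomized". The arm is therefore known to family and investigator before Visit 2 takes place.

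The schedule in the synopsis describes Visit 2 as "Status evaluation, possible prescription of antibiotics", and section 10.2 leaves the antibiotic judgement to the investigator. For the main criterion, protocol section 12.2.2 and the SAP both say "Scores will be evaluated by treatment and time point, i.e. per visit". The second part of that criterion is the number of patients per treatment who need an antibiotic.

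The entry criterion in section 9.2 is "Possibility to initiate therapy within 72 hours since the onset of the disease symptoms". The Visit 1 assessments listed in section 10.1 do not name onset date and time as an item.

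No section asks for the Visit 2 or Visit 4 appointment to be made before allocation, for actual visit day to be shown by arm, or for actual visit time or time since onset to be used in the analysis. Analysis specifications are left until after the database is closed (protocol section 12.2 and SAP).

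**The concern.** Children with acute tonsillitis can be expected to improve over these days in either arm, so a child seen on day 4 will on average look better than the same child on day 2. If the date inside the window is agreed once the arm is known, the two arms can drift to different mean visit days. This needs no bad faith. A family or clinician may want an earlier look at a child without the add-on, or may be content to wait longer with one who has it.

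A comparison labelled by visit would attribute the resulting difference to the drug. The antibiotic judgement made at that visit is exposed in the same way. As written, the plan neither prevents such a drift nor would show it in the report.

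**Working it through.** **Inputs from the documents**
- Visit 2 on day 3 ± 1, so about 24 to 72 hours after Visit 1 (sections 8.5 and 10.2).
- Visit 4 on day 10, which is 9 days after Visit 1.
- Two-sided 5% test, 97 per group before dropout and 100 after, success 75% against 90%, difference 15 points (synopsis, sample size table).
- Onset to entry: 0 to 72 hours (section 9.2).

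**The plan's own figure.** (1.96 + 0.84)² / 0.15² × (0.75 × 0.25 + 0.90 × 0.10) = 96.7, rounded up to 97. It reproduces and is not in question. The 15-point difference serves here only as a yardstick.

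**Size at Visit 2, by assumption.** Suppose there is no drug effect, 100 children per arm, and success at Visit 2 in the earlier-seen arm of 30%, 50% or 75%. The false difference is recovery per day × gap in mean visit day. The rejection probability is that of the pooled two-sided z-test:

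Φ((d − 1.96·se₀)/se₁) + Φ((−d − 1.96·se₀)/se₁), with se₀ = √(2p̄(1 − p̄)/n) and se₁ = √((p₁(1 − p₁) + p₂(1 − p₂))/n).

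Example: p₁ = 0.50, p₂ = 0.55, n = 100 gives se₀ = 0.0706, se₁ = 0.0705 and a rejection probability of 0.105 + 0.004 = 0.109.

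| Assumed recovery per day | Quarter-day gap | Half-day gap |
|---|---|---|
| 5 points | 1.25 points, about 5% | 2.5 points, 6–7% |
| 10 points | 2.5 points, 6–7% | 5 points, 11–14% |
| 15 points | 3.75 points, 8–10% | 7.5 points, 19–25% |

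Percentages are false-positive rates over the three success levels, against a nominal 5%.

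**A second model.** Assume constant-rate recovery from Visit 1 that reaches 75% success at Visit 4. The plan gives no time point for its 75%, so this is a further assumption.
- Rate: ln(4)/9 = 0.154 per day.
- Visit 2: success 1 − e^(−0.154×2) = 26.5%, rising about 11 points per day. A half-day gap compares 23.6% at 1.75 days with 29.3% at 2.25 days, a difference of 5.7 points.
- Visit 4: the same gap compares e^(−0.154×8.75) = 0.260 with e^(−0.154×9.25) = 0.241, a difference of 1.9 points.
- If recovery is linear instead, half a day is worth 0.5 × 75/9 = 4.2 points at either visit.

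**Time since onset.** If uniform over 0 to 72 hours, its SD is 72/√12 = 20.8 hours. The standard error of the difference in arm means at 100 per arm is 20.8 × √(2/100) = 2.9 hours, so chance imbalance is about ±6 hours (95%). For precision, assume the Local Tonsillitis Manifestation total falls 1 to 1.5 points per day with SD 3.5 to 2.5. Onset time (SD 0.866 day) would then explain between (1 × 0.866)²/3.5² = 6% and (1.5 × 0.866)²/2.5² = 27% of the variance at Visit 2. None of these slopes or SDs is in the documents.

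**The case against.** A one-day tolerance is ordinary, both arms already share the day 3 target, and no section says that dates are picked by arm. All of this stands: the point concerns an opening left by the plan, not a defect shown to have operated. Half a day in the mean requires, for example, half of one arm to be seen a day later than it would have been in the other. A full day requires every child to be shifted, which is close to the extreme, and nothing in the documents suggests it.

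Three stronger readings are tempting and are not supported.
- **That the 0 to 72 hour entry range biases the comparison.** Added to the visit window, it spreads illness age at Visit 2 over about 24 to 144 hours. But time from onset to entry is fixed before randomization and is balanced in expectation. It adds noise and chance imbalance; only the visit date, set after allocation, opens a route to bias.
- **That the date of Visit 2 determines the antibiotic result.** Antibiotic need is counted per patient, and section 8.5 allows unscheduled visits for worsening or persistent symptoms. A later Visit 2 need not lower the total. The synopsis definition of success includes absence of an indication for antibiotics, so a Visit 2 judgement may carry forward, but its size cannot be worked out from the documents.
- **That the analysis rules out adjustment for timing.** The specifications are deferred, so timing is unspecified rather than excluded.

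It is also fair to say that the unblinded investigator scores symptoms and decides on antibiotics, a more direct source of bias that booking dates does not touch. That does not weaken the case for closing this smaller opening at almost no cost.

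**Conclusion.** The point holds as a cheap improvement. Visit 2 timing can differ between arms after open allocation, the plan does not guard against it, and the report as planned would not reveal it. Under assumed recovery of 5 to 15 points per day, a half-day difference in mean visit day would produce a false difference of about 2.5 to 7.5 points at Visit 2, against a planned 15. At Visit 4, which section 8.5 treats as the final evaluation, the direct effect is small, about 2 points under the constant-rate model. These sizes rest on assumed recovery rates and assumed gaps; whether any gap would arise is unknown.

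Using time since onset as a covariate is a separate matter of precision. It is valid because the variable precedes randomization, but the gain is unverified. Children still severe at 72 hours may be slower to recover, which could weaken the relation.

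**What to change.** 1. In sections 8.5 and 10.1, require the Visit 2 and Visit 4 dates to be booked and entered in the CRF before the allocation is opened. The window and the unscheduled visits for worsening stay as they are.
2. In the SAP, tabulate actual visit day (hours from Visit 1) by arm for Visits 2 and 4.
3. For precision only: record onset date and time at Visit 1, which the entry criterion already requires to be established, and prespecify hours from onset to Visit 1 as a baseline covariate in the between-arm models.

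Do not add an analysis restricted to children seen on their booked day. Keeping the appointment happens after randomization and may depend on arm and on worsening, so the restriction could itself introduce bias.

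The cost is a few CRF entries and a sentence or two in each document, with no extra visits or patients and slightly less freedom in booking.

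A separate task is to reconcile the statements on early evaluation: day 3 ± 1 in sections 8.5 and 10.2, day 3 without a window in the synopsis schedule, an evaluation 36–48 hours before active treatment in the synopsis entry on treatment duration, and "In the absence of positive effect within 36-48 hours from the beginning of treatment" in section 6.1. Which timing is right is not judged here; whatever window remains, the date should be booked before allocation.
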